2 PROTOCOL SUMMARY

Protocol Number: AKB-9778-CI-5001

Protocol Title: Phase 2 Double-masked, Placebo-Controlled Study To Assess The Safety And Efficacy Of Subcutaneously Administered AKB-9778 15mg Once Daily Or 15mg Twice Daily For 12 Months In Patients With Moderate To Severe Non-Proliferative Diabetic Retinopathy

Study Objectives:	
Primary Objective:
 
1. To assess the effects of AKB-9778 15mg once daily or 15mg twice daily for 12 months on severity of diabetic retinopathy in subjects with moderate to severe non-proliferative diabetic retinopathy (NPDR) 
Secondary Objective:
 
1. To assess the safety and tolerability of AKB-9778 15mg once daily or 15mg twice daily for 12 months in subjects with moderate to severe NPDR2. To determine the AKB-9778 systemic exposure based on sparse PK sampling in subjects with NPDR 
Exploratory Objectives:
 
1. To explore the potential benefit of AKB-9778 on renal function in subjects with NPDR2. To explore the relationship between AKB-9778 systemic exposure and efficacy and safety in subjects with NPDR 
Exploratory Efficacy Sub Study Objectives (To be conducted at a subset of sites)
 
1. To explore the effects of AKB-9778 on optical coherence tomography angiography (OCT-A) in subjects with NPDR2. To explore the effects of AKB-9778 on retinal function as measured by electroretinogram (ERG) assessment in subjects with NPDR3. To explore the effects of AKB-9778 on peripheral retinal abnormalities using ultra-wide field (UWF) fundus photography and UWF fluorescein angiography
Study Endpoints:	
Primary Efficacy Endpoint
 
1. Percentage of subjects with an improvement in study eye severity of diabetic retinopathy (DR) (Early Treatment Diabetic Retinopathy Study (ETDRS) DR Severity Score or DRSS) of ≥ 2 steps at Month 12 
Secondary Efficacy Endpoints
 
1. Mean change from baseline in DRSS in the study eye at Month 122. Patient level (binocular) change from baseline in DRSS (according to methods of Klein et al, 2001) at Month 123. Proportion of subjects with a worsening in the study eye DRSS of ≥ 2 steps at Month 124. Proportion of subjects with an improvement or worsening in the study eye DRSS of ≥ 3 steps at Month 125. Proportion of patients developing center-involved DME or PDR or PDR-related outcomes during study6. Primary and secondary endpoints (1 through 4) assessed at Months 3, 6 and 97. Primary and secondary assessments in all fellow eyes, fellow eyes that meet all eligibility criteria (qualified fellow eyes), and either eyes (i.e. best response)

	
Exploratory Efficacy Endpoints:
 
1. Change from baseline in urine-albumin-to-creatinine ratio (UACR) and estimated glomerular filtration rate (eGFR) at Month 12 
Exploratory Efficacy Sub-Study Endpoints:
 
1. Mean change from baseline in ERG parameters at Month 122. Mean change from baseline in indices of macular perfusion, as measured by OCT-A, at Month 123. Mean change from baseline in area of peripheral non-perfusion, peripheral leakage, and peripheral retinopathy using UWF imaging, at Month 12 
Safety Endpoints:
 
1. Incidence and severity of systemic and ocular adverse events (AEs)2. Change from baseline in body system assessments3. Change from baseline in vital sign measurements4. Change from baseline in ECG parameters5. Change from baseline in clinical laboratory assay results (blood chemistry, hematology, fecal occult blood and urinalysis)6. Change from baseline in intraocular pressure (IOP)7. Change from baseline in slit lamp examination parameters8. Change from baseline in dilated funduscopic examination parameters9. Change from baseline in fluorescein angiogram (FA) parameters10. Mean change from baseline in ETDRS Best Corrected Visual Acuity (BCVA) letter score in the study eye at Month 1211. Proportion of subjects with a decrease of ≥ 15 letters in ETDRS BCVA at Month 12 (compared to baseline)
Study Population:	Subjects with moderate to severe NPDR (ETDRS Level 43 – 53 inclusive), 18 through 80 years of age (inclusive), no evidence of central involved DME and ETDRS BCVA letter score ≥ 70 (Snellen 20/40 or better).
Study Design:	Phase 2 randomized, double-masked, placebo controlled, multi-center study, to evaluate the safety and efficacy of 12 months of subcutaneous AKB-9778 administered either 15 mg QD or 15 mg BID in subjects with moderate to severe NPDR. Pharmacokinetic assessments are included as an exploratory endpoint. Exploratory efficacy assessments (OCT-A, UWF imaging and non-invasive ERG) will also be included at a subset of sites. Blood samples will be retained for biomarker and genetic analysis.
General Statistical Methods and Types of Analyses:	
Analysis Populations
 
Safety Population
 
The safety population will include all enrolled subjects who receive at least one dose of study medication. All safety analyses will be conducted using the safety population.
 
Modified Intent-to-Treat Population
 
The modified intent-to-treat (MITT) population will include all enrolled subjects who receive at least one dose of study medication. The primary efficacy analysis will be conducted using the MITT population.
 
Per Protocol Population

	
The per protocol (PP) population will consist of all subjects in the MITT population who do not have major protocol deviations considered to affect the primary efficacy variable DRSS, have completed a minimum of 12 months of treatment and have been at least 70% compliant. Sensitivity analyses of the primary efficacy variables will be conducted using the PP population.
 
Sample Size
 
Estimates for sample size calculations are derived from published data from the analysis of the effect of ranibizumab (Lucentis®) and aflibercept (Eylea®) intravitreal administration regimens on DR severity score in the RISE/RIDE studies and VIVID/VISTA studies, respectively, in which 28-46% of subjects improved by \geq 2 steps after 12 months of treatment.
 
With 45 evaluable subjects per treatment group, the study has $> 85\%$ power (based on Fisher's Exact Test and a 2-sided alpha =0.05) to demonstrate a statistically significant improvement in proportion of subjects improving by \geq 2 steps on the ETDRS severity scale, assuming underlying rates for active and placebo of 30% and 5%, respectively. Assuming 10% drop-out/non-evaluable rate, a sample size of 50 subjects per treatment arm (approximately 150 total) has been selected.
 
Efficacy Analyses
 
All efficacy data will be summarized by treatment group and time point using appropriate descriptive statistics. Summaries will be presented for both the MITT and PP populations. The primary hypotheses to be tested is that AKB-9778 15mg twice daily and AKB-9778 15mg once daily will be superior to placebo in the improvement of DR as measured by the ETDRS severity scale change from baseline at 12 months. The primary hypotheses will be tested in the MITT population using a Fisher's Exact Test with a 2-sided 5% significance level. To adjust for multiplicity, a pre-specified testing order will be used. AKB-9778 15mg twice daily will be tested first, and AKB-9778 15mg once daily will be tested second. Secondary and exploratory endpoints will be analyzed without adjustment for multiplicity. Continuous variables will be analyzed using ANCOVA models and dichotomous variables will be analyzed using the same approach as outlined for the primary endpoint. Additional exploratory analyses will be conducted to understand the relationship between exposure and response.
 
Interim Safety Analyses
 
On an ongoing basis throughout the conduct of the study, multiple layers of planned safety monitoring will be conducted. These include weekly masked reviews by the Aerpio Medical Monitor, monthly masked reviews by the Aerpio Clinical Safety Review Team (CSRT), and quarterly masked reviews by the Safety Assessment Committee. These reviews are detailed in a separate document (AKB-9778 Safety Surveillance Plan).

Study Medication:	
Subcutaneous treatments:
 
• 15 mg AKB-9778 (in 100 mg/mL Hydroxypropyl-Beta-Cyclodextrin [HPβCD]) subcutaneous injection: To be provided as sterile pre-filled ready-to-inject syringes• Placebo (Phosphate-Buffered Saline) subcutaneous injection: To be provided as sterile pre-filled ready-to-inject syringes
Duration of Treatment:	48 weeks
Duration of Participation:	Screening period: up to 4 weeks; Baseline and Treatment period: 48 weeks; Post-treatment Follow-up period: 4 weeks. The Screening, Baseline, Treatment, and Follow-up periods will require subject participation for approximately 56 weeks.
Number of Subjects:	Approximately 150 subjects (50 per treatment group)

Number of Study Centers:	Approximately 50 sites
Volume of Blood Drawn:	Hematology (8 X 4 mL) Chemistry (14 X 3.5 mL) Serum Pregnancy (1 X 2.5 mL) Pharmacokinetic Samples (4 X 6 mL) Exploratory Biomarker (2 X 3 mL) Genetic Sample (1 X 8.5 mL) Total volume blood drawn for entire study: Approximately 134 mL per subject.

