7.6 Discontinuation of Study Medication/Withdrawal of Subjects

Subjects will discontinue study medication for any of the following conditions:

- In the opinion of the Investigator, it is medically necessary
- The subject withdraws consent
- Major toxicity considered to be related to study medication
- The investigator obtains the treatment code for the subject
- Administrative reasons, such as, subject non-compliance or a major protocol violation
- Upon request of the Subject, Sponsor, Institutional Review Board (IRB) or regulatory agency
- Study termination

In addition to the above reasons for study medication discontinuation, if the subject meets criteria for treatment of PDR or DME (e.g. Anti-VEGF, steroids, laser, vitrectomy) in the study eye or qualified fellow eye, study medication may be discontinued at the discretion of the principal investigator and the subject.

- *Criteria for treatment of PDR or DME in the study eye or qualified fellow eye are given in [Appendix B](#). Non-qualified fellow eyes may be treated at the discretion of the Investigator.*
- *Refer to [Section 8.4.3](#) for additional details regarding assessments to be conducted prior to treatment of PDR or DME.*

Once it is identified that a subject will discontinue study medication, the subject should undergo all EOT (Month 12/Early Withdrawal) assessments (See [Section 9.3.2.16](#)) as soon as possible after study medication is stopped. The subject will then enter the 1-month Follow-up period provided that the subject has not withdrawn consent.

If a subject does not return for a scheduled site visit or complete a homecare nurse visit, every effort should be made to contact the subject. In any circumstance, every effort should be made to document subject outcome by completing the End of Treatment (Month 12/ Early Withdrawal) assessments.

The Investigator must document the primary reason for discontinuation of study medication on the appropriate case report form (CRF). If the reason for discontinuation of study medication is a clinical AE, monitoring will continue until the AE resolves or the Investigator assesses the AE as chronic or stabilized.

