#### **5.2 Secondary Efficacy Endpoints**

Secondary efficacy endpoints include:

- Proportion of subjects with a worsening in the study eye DRSS of  $\geq 2$  steps at week 48
- Mean change from baseline in DRSS in the study eye at week 48
- Proportion of subjects with an improvement or worsening in the study eye DRSS of  $\geq 3$  steps at week 48.
- Subjects with criterion step improvement in DRSS at week 48 ( $\geq 2$  steps improvement in the study eye for patients with non-qualified fellow eye and  $\geq 3$  steps improvement on the Person scale for patients with qualified fellow eyes)
- Subjects with criterion step improvement in DRSS at week 48 ( $\geq 2$  steps improvement in the study eye for patients with non-qualified fellow eye and  $\geq 3$  steps improvement on the Binocular scale for patients with qualified fellow eyes)
- Proportion of patients developing center-involved Diabetic Macular Edema (DME) or Proliferative Diabetic Retinopathy (PDR) or PDR-related outcomes during treatment period based on Clinical Data. Due to variation in clinician criteria for reporting DME and PDR adverse events, all events will be reviewed and AEs that were not treated and were not validated in FPRC interpretation of imaging data will be censored from the results.
- Proportion of patients developing center-involved DME or PDR or worsening of  $\geq 2$  steps DRSS at week 48 based on Central Image Reading Center Evaluation
- Primary and secondary assessments in qualified fellow eyes and all qualified eyes (study eyes and qualified fellow eyes).

- Primary and secondary endpoints assessed at week 12, 24 and 36.

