## **10.1 Primary Efficacy Endpoint Analysis**

The primary hypotheses to be tested is that AKB-9778 15 mg twice daily and AKB-9778 15 mg once daily will be superior to placebo in the improvement of DR as measured by the ETDRS severity scale change from baseline at 48 weeks. Specifically, the primary endpoint is the percentage of subjects with an improvement in study eye severity of DR (ETDRS DRSS) of  $\geq 2$  steps at 48 weeks without need for treatment of PDR or DME (by IVT, laser, or vitrectomy) in the study eye. DRSS scores used for all analyses will be obtained from final adjudicated grading by the central reading center (Fundus Photograph Reading Center for the standard field images).

The primary hypotheses will be tested in the MITT population using a Fisher's Exact Test with a 2-sided 5% significance level. AKB-9778 15 mg twice daily will be tested first. If this is found to be statistically significant, then AKB-9778 15 mg once daily will be tested for statistical significance, at the same significance level. Cochran-Mantel-Haenszel (CMH) test stratified for baseline ETDRS DRSS (levels 4, 5 and 6) will also be used for testing primary hypothesis in the MITT population. Missing data will be imputed using LOCF; baseline values will not be carried forward.

As a sensitivity analysis, primary hypothesis will be tested using Fisher's Exact test, and CMH test stratified for baseline ETDRS DRSS (levels 4, 5 and 6) on OC in the PP population.

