## **10.2 Secondary, Exploratory and Exploratory Sub-Study Efficacy Endpoint Analysis**

Secondary efficacy endpoints are summarized in Section 5.2, and involve alternative analyses of DRSS results, showing the proportion of patients who develop sight-threatening complications of DR (DME & PDR). Measures of kidney function (UACR and eGFR) are exploratory efficacy endpoints. Exploratory sub-study endpoints are derived from OCT-Angiography, Ultra-wide field fluorescein angiography, Ultra-wide field color photographs, and electroretinography. Details of these variables and their analysis are contained in separate SAPs.

Normality assumption will be tested for any endpoint of continuous nature. If normality assumption is violated, appropriate transformation and/or non-parametric analysis will be employed. Otherwise, all secondary, exploratory and exploratory sub-study endpoints of continuous nature will be analyzed using ANCOVA model, and all inferential analyses will use a 2-sided 5% significance level. For the exploratory efficacy endpoints UACR and eGFR, for internal decision-making purposes, a 1-sided 10% significance level will be used. Whenever possible, a mixed model repeated measures (MMRM) model will be utilized to analyze this data. The model will include change from baseline as the dependent variable. The p-value and 95% CI from the model is baseline parameter adjusted.

For MMRM, visit will be treated as the repeated variable within a subject. Within-subject error, an unstructured variance-covariance will be applied; in case of non-convergence, compound symmetry will be used. MMRM model for UACR and eGFR is adjusted by the baseline HbA1c, Baseline Systolic BP, log-transformed Baseline UACR, and ACEi/ARB use.

Secondary, exploratory and exploratory sub-study endpoints of a dichotomous nature will be analyzed using the same approach as outlined for the primary efficacy endpoint.

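### The DME/PDR progression endpoint is an event over follow-up but is compared as a crude proportion; early leavers count as event-free, which slightly understates incidence and creates a false arm difference only if drop-out differs between arms

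*Protocol*

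**What the plan says.** Protocol 2 lists the secondary endpoint as "Proportion of patients developing center-involved DME or PDR or PDR-related outcomes during study"; Protocol 5.6 is nearly the same. SAP 5.2 changes the period: "Proportion of patients developing center-involved Diabetic Macular Edema (DME) or Proliferative Diabetic Retinopathy (PDR) or PDR-related outcomes during treatment period based on Clinical Data". The note to file attached to the SAP counts a qualified eye as a progressor if any of six conditions occurred in the trial. Two of these (CST increase of at least 20%, DRSS above 53) are read at the last observation, whenever that falls.

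On analysis, SAP 10.2 states: "Secondary, exploratory and exploratory sub-study endpoints of a dichotomous nature will be analyzed using the same approach as outlined for the primary efficacy endpoint". SAP 10.1 tests the primary endpoint in the MITT population "using a Fisher's Exact Test with a 2-sided 5% significance level", adds a CMH test stratified by baseline DRSS, and fills gaps by LOCF without carrying baseline forward.

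On follow-up, a subject who stops study medication has the end-of-treatment assessments early. Protocol 7.6 continues: "The subject will then enter the 1-month Follow-up period provided that the subject has not withdrawn consent". Protocol 9.3.3.6 shows that visit as a home-nurse visit with medical history and body systems only, and no retinal examination or imaging.

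No Kaplan-Meier, log-rank, Cox or person-time analysis appears in either document. Where SAP 5.2 speaks of censoring, it means dropping unconfirmed adverse events, not ending a subject's time at risk.

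**The concern.** Developing DME or PDR has a date, and subjects are watched for it over different lengths of time. A fixed yes/no gives a subject who leaves at Month 2 without an event the same weight as one followed event-free for 48 weeks. LOCF does not correct this, because carrying forward no event so far amounts to no event by Week 48. If one arm loses more subjects, that arm looks better without any drug effect; if placebo loses more, a true effect is diluted. SAP 10.2 presents this endpoint as capturing sight-threatening complications, so readers will take its incidence at face value.

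**Working it through.** **The plan's own figure.** The only power statement concerns the primary endpoint (Protocol 11.1, SAP 3.1): 45 evaluable per arm, 30% versus 5%, two-sided Fisher at 5%. Exact enumeration gives 86.3%, so the stated power above 85% is confirmed, and 45/0.9 = 50 per arm. No event rate or power is given for the DME/PDR endpoint.

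**Inputs.** From the documents: 50 per arm, 48 weeks of treatment, 10% drop-out with no split by arm. Assumed: true 48-week risk p of 10% to 30%, constant hazard, exit uniform over 48 weeks and unrelated to progression, and an illustrative 20% versus 5% drop-out split.

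**Formula.** With λ = −ln(1−p), a leaver has an event before exit with probability m = 1 − p/λ. With drop-out d:
- crude risk = (1−d)p + d·m
- understatement in an arm = d(p−m)
- false difference between arms with equal true risk = (d₁−d₂)(p−m)

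| p | λ | m | p−m | understatement, d = 10% | false difference, 20% vs 5% |
|---|---|---|---|---|---|
| 10% | 0.1054 | 5.1% | 4.9 points | 0.5 | 0.15 × 4.9 = 0.7 |
| 20% | 0.2231 | 10.4% | 9.6 points | 1.0 | 0.15 × 9.6 = 1.4 |
| 30% | 0.3567 | 15.9% | 14.1 points | 1.4 | 0.15 × 14.1 = 2.1 |

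At p = 20% the crude risks are 0.80 × 20% + 0.20 × 10.4% = 18.1% and 0.95 × 20% + 0.05 × 10.4% = 19.5%. At p = 30% they are 27.2% and 29.3%. Simulation with events dated to visits gives 18.1% versus 19.6-19.7%, and 27.2% versus 29.3%. With equal drop-out the false difference is zero.

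**More extreme splits.** At 10% versus 30% drop-out the false difference is 1.0-2.8 points with uniform exit, and 1.5-4.3 points if all exits fall at week 12.

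**Against sampling error.** At p = 20% the standard error of the difference is √(0.181×0.819/50 + 0.195×0.805/50) = 7.8 points.

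**Fisher's type I error at 50 per arm.** With no drop-out it is 2.8% (p = 20%) and 3.1% (p = 30%). For the 20% versus 5% split it stays at 3-4%. The worst case examined (p = 30%, 10% versus 30% drop-out, all exits at week 12) is 5.1%.

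**With a true effect, 30% placebo versus 15% active.** Equal 10% drop-out gives 28.6% versus 14.3%. The 15.0-point difference shrinks to 14.3, while the risk ratio stays near 0.50. With 10% placebo and 30% active drop-out the difference is 15.8 points; with the reverse it is 11.5. Fisher's power is 33%, 41% and 22% respectively, against 35% with no drop-out.

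**With censoring at exit.** For 10% versus 30% drop-out and exact event dates, Kaplan-Meier returns 20.0% and 20.1% at true 20%, and 30.1% and 29.9% at true 30%. Log-rank size is 4.9-5.1%. With events dated only to visits and the 20% versus 5% split, Kaplan-Meier gives about 20.5% versus 20.3%, and 30.7% versus 30.2%.

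**Power at equal 10% drop-out,** for true risks of 25% vs 10%, 20% vs 5% and 30% vs 10%: Fisher 39%, 47%, 61%; an unstratified Mantel-Haenszel test (the type of the planned CMH) 48%, 62%, 69%; log-rank 49%, 63%, 70%.

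**The case against.** The case against acting is substantial, and most of it limits the point without removing it.

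- **Equal drop-out.** The plan assumes a single 10% rate. At that rate there is no false difference, and no passage predicts an unequal split. This stands.
- **Size.** A reader might infer a real risk of a false claim that the drug prevents DME or PDR. The numbers do not support that: the shift is small beside a standard error near 8 points, and Fisher's test stays conservative in the 20% versus 5% case.
- **Power.** A reader might infer that a survival analysis gains power. It does so against Fisher, but the planned CMH-type test is within about a point of log-rank at equal drop-out.
- **Cause.** Injection burden is a tempting reason for more active-arm exits. Protocol 6.1 rules it out: all three arms inject twice daily.
- **Informative exits.** Rescued eyes are failures (SAP 7.2), treated DME/PDR counts as an event (note to file), and leavers are asked for full end-of-treatment imaging (Protocol 7.6, 8.4.3). Only event-free leavers are affected.
- **Target.** If the aim is events while treated, the crude proportion estimates that directly. It is understated only as a 48-week risk, and the SAP does not say which is meant.
- **Inference.** The documents never state that leavers are event-free; this follows from LOCF and the progressor definition. SAP 5.2 also has a reading-centre version fixed at Week 48, where a leaver with no post-baseline image may be missing instead.

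What remains is that the plan has no rule for shortened follow-up on an event endpoint, and that dated data to handle it are already collected.

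**Conclusion.** The point holds as a modest gap in estimation. Read as a 48-week risk, the crude proportion is about 1 point low per arm at 20% risk and 10% drop-out. A false arm difference needs unequal drop-out, and is about 1.5 to 2 points for a 20% versus 5% split at risks of 20% to 30%, with no material inflation of Fisher's type I error. At equal drop-out a true difference shrinks slightly (15.0 to 14.3 points in the example).

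These sizes rest on assumed event rates, constant hazard, uniform exit and exit unrelated to progression. The endpoint is secondary and not adjusted for multiplicity, and the primary analysis is unaffected. The change is worth making because it is cheap and because the direction of any distortion depends on which arm loses more subjects, which cannot be known in advance.

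**What to change.** In SAP 5.2 and 10.2:

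1. Add a time-to-first-event analysis of the clinical-data endpoint, from Day 1 to adverse-event onset or date of PDR/DME treatment, censored at the last on-study eye examination.
2. Report Kaplan-Meier 48-week incidence per arm, the difference from placebo with 95% CI, and a log-rank test stratified by randomisation DRSS level.
3. Keep the note-to-file definition for the CST and DRSS components read at the last observation. Date them to that last visit and note that they are interval-censored. Dating them to first occurrence would change the endpoint.
4. Report follow-up time by arm, keep the crude proportion alongside, and state how leavers are counted in it.
5. Reconcile the protocol's study period with the SAP's treatment period.

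The cost is SAP wording and one survival program, with no new data. There are two downsides. Censoring assumes that exit for reasons other than PDR/DME is unrelated to progression. Imaging events are dated only to quarterly visits, which left a small opposite shift of 0.2 to 0.5 points (20.5% − 20.3%; 30.7% − 30.2%) in the simulation above.
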